5 ANALYSIS POPULATION

5.1 Enrolled patients

All patients enrolled in this study.

5.2 Analysis population

Enrolled patients who meet all the inclusion criteria.

6 DATA HANDLING

6.1 Handling of omitted or missing data

- If date data is missing, it will be handled as follows:
 - If "year" is unknown, it will be treated as missing.
 - If "month" is unknown, July will be used.
 - If "date" is unknown; 15th will be used
 - If "month and date" are unknown, 1st July will be used.
- Except as noted above, missing values will not be supplemented.

- If the above supplementation results in reversal of days in the calculation of the number of days (e.g., the number of days from the start of treatment to the end of treatment), it will not be adopted in the analysis.

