## 6. MILESTONES

Milestone	Planned date
Observation period	from index date to 20 Jun 2021
Start of data collection	08 Sep 2021
End of data collection	31 Jan 2022
Analytical dataset lock	31 Jan 2022
Final study report	31 May 2022

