#### **9.1.3.2. Real-world PFS**

Real-world PFS is defined as the following:

- Real-world PFS, defined as time from start of avelumab/axitinib treatment to date of first disease progression (as clinically assessed by local investigator based on radiology, laboratory evidence, pathology, or other assessments) or death due to any cause, whichever came first  
If there were no clinical records of death or disease progression, they were censored at the date of initiation of the next line of therapy for the patients undertaking two or more lines of therapy based on the record, or at their last visit date during the study period for the patients undertaking only one line of therapy based on the record.

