## **9.6. Data management**

Investigators will fill out electronic case report forms (eCRFs) based on the medical charts by electronic data capture (EDC). After the completion, eCRFs are transferred to a single electronic database. Only the de-identified and anonymized data are included.

When receiving a query from the sponsor on the completed eCRF (ie, Data Clarification Form [DCF]), investigators will reconfirm the information on source documents, fill out the DCF as required, and submit the DCF.

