- 5) Deceased patients are also included for inclusion criteria 1-3.

➤ Exclusion criteria

- There are no exclusion criteria for this study.

5) Study size

This study is descriptive study which aims to describe the demographic and baseline characteristics of patients who were treated avelumab plus axitinib in first-line treatment for mRCC, rather than testing any pre-defined hypothesis. Since all the analyses will be descriptive, sample size calculations are not applicable.

The expected number of patients will be approximately 70 patients in total, but the number should be considered flexible.

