6.3 Derivation variables

1) Survival time analysis

It is defined as follows:

Endpoint	Start date	End date (event)	End date (censor)
Real-world PFS	Date treatment with avelumab and/or axitinib was initiated (if not on the same day, whichever occurs earlier)	Date of first disease progression (clinical evaluation based on radiological, laboratory, pathological, or other evaluation by the principal investigator) or death from any cause, whichever occurs earlier	Date of last confirmation of progression-free survival or start of subsequent treatment (whichever occurs earlier)
TTF of avelumab and axitinib	Date treatment with avelumab and/or axitinib was initiated	Date of completion of treatment with avelumab and/or axitinib	Date of last confirmation of progression-free survival or date of last dose in case of efficacy stopping (whichever date occurs earlier)
TTF of avelumab	Date treatment with avelumab was initiated	Date of completion of treatment with avelumab	Date of last confirmation of progression-free survival or date of last dose in case of efficacy stopping (whichever date occurs earlier)
TTF of axitinib	Date treatment with axitinib was initiated	Date of completion of treatment with axitinib	Date of last confirmation of progression-free survival or date of last dose in case of efficacy stopping (whichever date occurs earlier)

2) Objective response rate

ORR is defined as the proportion of patients with a CR or PR as the best overall response in tumor assessment during the observation period, as assessed by an investigator under actual clinical practice, including assessment based on RECIST ver. 1.1.

3) Calculation of duration

Duration	Definition
Duration of avelumab treatment	Date of last dose – date of initial dose + 14
Duration of axitinib treatment	Date of last dose – date of initial dose + 1
Duration of non-administration	Date of end – Date of start + 1

4) Corticosteroid equivalent dose (prednisolone equivalent)

This will be calculated as shown in the table below.

Generic name	Corresponding amount (mg)	Prednisolone conversion ratio
Cortisone	25	0.2
Hydrocortisone	20	0.25
Prednisolone	5	1
Methylprednisolone	4	1.25
Triamcinolone	4	1.25
Dexamethasone	0.75	6.7
Betamethasone	0.6	8.3

5) Date of initial dose

If avelumab and axitinib are administered for different durations, the earlier of the two dates should be used as the date of the initial dose.

6) Date of last confirmation of progression-free survival

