8.3.3.3 Duration of corticosteroids treatment for irAE during avelumab plus axitinib treatment

Analysis set	Analysis population
Details of analysis	Perform the same analysis as in 8.3.3.2 for duration of corticosteroid treatment.
Supplement	If the patient is on continuous corticosteroid treatment, the period should be up to the cut-off date (20 June, 2021).

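### SAP 6.1 sets unknown months to July without bounding the date by treatment start or by 20 June 2021, so in-window 2021 events land after observation ended and some year-only 2020 events are lost

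*SAP*

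**What the plan says.** SAP 6.1 treats a date with unknown year as missing. An unknown month becomes July and an unknown day becomes the 15th; when both "are unknown, 1st July will be used". No other imputation is allowed. The one safeguard concerns order: if the filled-in date reverses a calculated duration, "it will not be adopted in the analysis". Nothing is put in its place.

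Observation runs "from index date to 20 Jun 2021" (Protocol 6), and treatment starts lie between 20 December 2019 and 20 December 2020 (SAP 4). Data collection runs from 8 September 2021 to 31 January 2022 (Protocol 6).

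The endpoint table in SAP 6.3 sets no calendar limit on event dates. Its censoring entry for real-world PFS is "Date of last confirmation of progression-free survival or start of subsequent treatment (whichever occurs earlier". Protocol 9.1.3.2 mentions the study period only for the censoring visit ("at their last visit date during the study period"). The SAP does apply the cut-off to continuing corticosteroid treatment, where "the period should be up to the cut-off date (20 June, 2021" (SAP 8.3.3.3).

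**The concern.** A mid-year default works when the whole year is feasible. Here neither main calendar year is. Follow-up in 2021 stops eleven days before 1 July, and almost half of the permitted 2020 start dates come after 1 July. The default therefore lies outside the feasible interval for all in-window 2021 events, and for all 2020 events in the later starters.

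The reversal check cannot see the 2021 problem, because July 2021 follows every permitted start. It does catch the 2020 problem, but discards the date rather than repairing it, so a failure within about six months of start stops counting as an event. What is at stake is the event times in the Kaplan-Meier analyses of TTF and real-world PFS, and treatment durations that rest on a partial last-dose date.

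**Working it through.** **Inputs.** Imputation and reversal rules: SAP 6.1. Start window: SAP 4. End of observation: Protocol 6. One month = 30.4375 days: SAP 6.2. The plan states no figure of its own to reproduce.

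**(a) 2021 events.**
- Possible in-window dates, 1 January to 20 June 2021: 31 + 28 + 31 + 30 + 31 + 20 = 171.
- With unknown month, every one is moved to 1-31 July 2021, which is 11 to 41 days after the cut-off.
- Year-only: the imputed 1 July is later than the true date by 11 days (true date 20 June) to 181 days (true date 1 January). The mean over equally likely dates is (11 + 181)/2 = 96 days, or 96/30.4375 = 3.2 months.

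**(b) Events before 2021.**
- Start dates: 12 in December 2019 plus 355 from 1 January to 20 December 2020 = 367.
- Starts after 1 July 2020: 30 + 31 + 30 + 31 + 30 + 20 = 172, and 172/367 = 46.9%. This is a share of dates, not of patients. A year-only 2020 event in any of these patients is reversed.
- The longest time to such an event is 2 July to 31 December 2020: 182 days, or 6.0 months.
- A year-only 2019 event (starts on 20-31 December 2019) is also reversed.
- For starts up to 1 July 2020, a year-only 2020 event is kept at 1 July and may be moved either way.

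**Handling of a discarded date.** SAP 6.3, item 6, deals with absent or unknown progression data by assigning a date of last progression-free confirmation. With the PFS censoring entry, this arguably turns the patient into a censored case. No comparable handling is stated for a treatment stop (TTF) or a death date.

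**Illustration of size.** Assumptions: uniform accrual over the start window; exponential event times with the 13.8-month median that Protocol 7 cites; year-only dates at random among events; no post-cut-off events recorded. In 1 million simulated patients, 44% have an in-window event, or about 31 of 70. Of these events, 41% are type (a), 15% are type (b), and 44% may move either way. Type (a) events are kept at 1 July 2021, as the text says. Type (b) patients are excluded, censored at the cut-off, or censored at the last event-free date.

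| Year-only share of events | Events of about 31 | Median under SAP 6.1 (months) | Bounded midpoint (months) |
|---|---|---|---|
| 0% | 0 | 13.8 | 13.8 |
| 5% | 1.6 | about 14.0 | 13.8 |
| 10% | 3.1 | 14.1-14.2 | 13.8 |
| 20% | 6.2 | 14.4-14.6 | 13.8 |

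For comparison, in simulated samples of 70 patients, 95% of the medians that were reached lay between 9.3 and 16.9 months. The median was not reached in 20% of samples.

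**If post-cut-off 2021 events are also recorded.** Suppose charts include events up to 15 November 2021, so that 40% of year-only 2021 events are late (assumed). The lowest SAP medians are then 13.7, 13.7 and 13.6 months at 5%, 10% and 20%. The error can therefore go either way.

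**The case against.** The strongest reply is that the trigger is rare. It needs an unknown month, not just an unknown day, for a 2020-2021 event in a site chart. Administration dates are collected for both drugs (Protocol 9.3.5 and 9.3.6), data are monitored remotely (Protocol 9.8), and on a query "investigators will reconfirm the information on source documents" (Protocol 9.6). The study is descriptive, and "The expected number of patients will be approximately 70 patients in total", so sampling variation exceeds the shifts above. All of this stands and limits the severity. It does not rescue the rule, which exists for the dates that queries cannot complete and misplaces or drops those described.

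Four stronger readings are tempting, and the documents do not support them:

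- **The rule lengthens PFS and TTF substantially.** Much longer medians, up to 16.6 months at 20% year-only, arise only if 2021 events imputed to July are then censored at the cut-off. The SAP states no such step. The net direction is not fixed either, as the last calculation shows.
- **The status of a patient with a discarded date is wholly undefined.** For real-world PFS there is an arguable default in SAP 6.3, item 6. The clear gap is in TTF and death dates.
- **The imputed 2021 dates are impossible.** July 2021 precedes data collection, so these dates are out of window, not impossible.
- **The primary endpoint is certainly untouched.** The IMDC score uses time from diagnosis to systemic therapy (Protocol 9.3.2). If that is derived from a partial diagnosis date, SAP 6.1 could reach it. The documents do not say how it is recorded.

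**Conclusion.** The concern holds. Followed as written, SAP 6.1 dates every in-window 2021 event with unknown month after observation ended, and removes as events the year-only 2020 failures of patients who started after 1 July 2020. These results follow from the calendar and need no model. Nothing in SAP 6.3, SAP 8.3.3.3 or Protocol 9.1.3.2 repairs them.

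The effect on the reported medians is unknown, because the documents give no count of partial dates. Under the illustrative assumptions it is about 0.2 months at 5% year-only events and 0.6 to 0.8 months at 20%, with the direction open if later 2021 events are in the charts. Severity is minor to moderate: a stated rule gives wrong dates in secondary analyses, probably for few patients.

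**What to change.** In SAP 6.1, for event and stop dates:

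1. Replace the fixed July date with the midpoint of the feasible interval. The lower bound is the later of (i) the start of the known year or month and (ii) the treatment start or last date known event-free. The upper bound is the earliest of the end of the known year or month, the next known date, and 20 June 2021. With no other information, a year-only 2021 event then goes to 27 March 2021, with a maximum error of 85 days instead of 181.
2. State that events after 20 June 2021 are not counted for TTF and real-world PFS.
3. Where other chart or eCRF data cannot place a year-only 2021 event before or after the cut-off, report the result both ways: counted at the bounded midpoint, and censored at the last date known event-free. Prespecify one as main. Simply censoring all such events is not a safe sole rule: under the late-recording assumption above, with none corroborated, it gives 14.2, 14.6 and 15.5 months against 13.8 at 5%, 10% and 20% year-only.
4. Use the bounded date in place of the non-adoption rule.
5. Report the number of imputed dates per endpoint.

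The cost is SAP wording, a short date routine and one extra sensitivity analysis. The midpoint remains approximate. Protocol 9.7.4 requires the SAP to be fixed before data lock, so the rule should be settled by then.

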6.2 Handling of days

- 1 week = 7 days
- 1 month = 30.4375 days
- 1 year = 365.25 days

6.3 Derivation variables

1) Survival time analysis

It is defined as follows:

Endpoint	Start date	End date (event)	End date (censor)
Real-world PFS	Date treatment with avelumab and/or axitinib was initiated (if not on the same day, whichever occurs earlier)	Date of first disease progression (clinical evaluation based on radiological, laboratory, pathological, or other evaluation by the principal investigator) or death from any cause, whichever occurs earlier	Date of last confirmation of progression-free survival or start of subsequent treatment (whichever occurs earlier)
TTF of avelumab and axitinib	Date treatment with avelumab and/or axitinib was initiated	Date of completion of treatment with avelumab and/or axitinib	Date of last confirmation of progression-free survival or date of last dose in case of efficacy stopping (whichever date occurs earlier)
TTF of avelumab	Date treatment with avelumab was initiated	Date of completion of treatment with avelumab	Date of last confirmation of progression-free survival or date of last dose in case of efficacy stopping (whichever date occurs earlier)
TTF of axitinib	Date treatment with axitinib was initiated	Date of completion of treatment with axitinib	Date of last confirmation of progression-free survival or date of last dose in case of efficacy stopping (whichever date occurs earlier)

2) Objective response rate

ORR is defined as the proportion of patients with a CR or PR as the best overall response in tumor assessment during the observation period, as assessed by an investigator under actual clinical practice, including assessment based on RECIST ver. 1.1.

3) Calculation of duration

Duration	Definition
Duration of avelumab treatment	Date of last dose – date of initial dose + 14
Duration of axitinib treatment	Date of last dose – date of initial dose + 1
Duration of non-administration	Date of end – Date of start + 1

4) Corticosteroid equivalent dose (prednisolone equivalent)

This will be calculated as shown in the table below.

Generic name	Corresponding amount (mg)	Prednisolone conversion ratio
Cortisone	25	0.2
Hydrocortisone	20	0.25
Prednisolone	5	1
Methylprednisolone	4	1.25
Triamcinolone	4	1.25
Dexamethasone	0.75	6.7
Betamethasone	0.6	8.3

5) Date of initial dose

If avelumab and axitinib are administered for different durations, the earlier of the two dates should be used as the date of the initial dose.

6) Date of last confirmation of progression-free survival

If there is no or unknown data of progressive disease (PD) in the [Progressive disease (PD) information] of the CRF, the date of diagnosis shall be the date of confirmation of the last progression-free survival.

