### **9.1.3. Definition of endpoints**

#### **9.1.3.1. Time to treatment failure (TTF)**

TTF is defined as the following:

- TTF, defined as time from start of avelumab/axitinib treatment to end of treatment for any cause earlier, including death.

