## **9.7. Data analysis**

Detailed methodology for summary and statistical analyses of data collected in this study will be documented in a statistical analysis plan (SAP), which will be dated, filed, and maintained by the sponsor. The SAP may modify the plans outlined in the protocol; any major modifications of primary endpoint definitions or their analyses would be reflected in a protocol amendment.

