9 CHANGES FROM THE PROTOCOL

Not applicable.

Last page

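### The SAP censors efficacy stops in all three time-to-treatment-failure rows, against the protocol's any-cause definition, and declares no change

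*SAP*

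**What the plan says.** Protocol 9.1.3.1 defines TTF as "time from start of avelumab/axitinib treatment to end of treatment for any cause earlier, including death". It exempts no stopping reason and gives no censoring rule. Protocol 9.1.2 lists TTF of the combination, of avelumab and of axitinib as secondary endpoints.

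SAP 6.3(1) gives all three the same censoring rule: "Date of last confirmation of progression-free survival or date of last dose in case of efficacy stopping (whichever date occurs earlier". The event for the combination is "Date of completion of treatment with avelumab and/or axitinib". The single-drug rows use completion of that drug. The PFS row of the table adds "or death from any cause, whichever occurs earlier"; the TTF rows do not name death.

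Two further items of SAP 6.3 bear on these rows. Item 5 says that, when the drugs are "administered for different durations, the earlier of the two dates should be used as the date of the initial dose". Item 6 defines the last progression-free confirmation for patients whose progression data are absent or unknown, and sets it to a date of diagnosis without saying which diagnosis.

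Protocol 9.7 states "The SAP may modify the plans outlined in the protocol" and requires an amendment only for major changes to primary endpoints. SAP Section 9, which lists changes from the protocol, reads "Not applicable".

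**The concern.** A last-dose date tied to a stopping reason has no function in the censoring column unless that stop is censored. The SAP therefore treats some ends of treatment as non-events, while the protocol counts them all. If efficacy stops occur, the reported TTF is not the protocol's TTF, and a reader has no notice of it. If the term covers lack of efficacy, true treatment failures are censored.

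Three lesser points sit in the same rows.

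- **Censoring date.** A progression-free date closes follow-up for a treatment endpoint. No protocol sentence forbids this, but the date measures the wrong status. A patient still on drug after progression falls outside the definition in SAP 6.3(6).
- **Combination end date.** *And/or* lets two different quantities be reported under one name.
- **Death not named.** This is wording only: an on-treatment death ends treatment, and SAP 8.3.6 captures the date of death.

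**Working it through.** **Text comparison**

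| Item | Protocol | SAP |
|---|---|---|
| Event | End of treatment, any cause, including death (9.1.3.1) | Completion of treatment (6.3(1)) |
| Efficacy stop | Event, because no reason is exempt | Censored at last dose |
| Declared as a change | Modification allowed (9.7) | None declared (Section 9) |

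The contradiction follows from the text and needs no assumption.

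**Inputs for size.** The plan states no expected TTF, so there is no figure to reproduce. From the documents: entry 20 December 2019 to 20 December 2020 and cut-off 20 June 2021 (Protocol 9.1), which is 182 to 548 days or, at 30.4375 days per month, 6.0 to 18.0 months; median PFS 13.8 months in the phase 3 trial (Protocol 7); about 70 patients (Protocol 9.5). Assumed: exponential times, uniform follow-up, other-cause stopping with median 24 months, and the efficacy-stop and confirmation frequencies below. Results are from 400,000 simulated patients.

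**1. Efficacy stops censored.** Efficacy stops are assumed due at months 6 to 15 in patients still progression-free.

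- 5% of patients due to stop (about 1 of 70 observed): 12-month TTF rises 1.3 to 1.4 points.
- 10% due (about 2 of 70 observed): it rises 2.6 to 2.8 points.
- If the term covers lack of efficacy and 10% or 25% of progression-driven stops are coded that way: it rises 2.2 to 2.4 or 5.9 to 6.2 points.

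A simpler check assumes that a fraction f of all stops is censored independently of time. The hazard is then multiplied by (1 − f), so median = true median / (1 − f) and 12-month rate = S^(1 − f). With a true median of 12 months (S = 0.50):

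- f = 5%: 12 / 0.95 = 12.6 months; 0.50^0.95 = 51.8%.
- f = 10%: 12 / 0.90 = 13.3 months; 0.50^0.90 = 53.6%.

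**2. Progression-free date used for censoring (no efficacy stops).** The time lost per on-treatment patient is about half the confirmation interval.

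| Confirmation every | Months lost | 12-month TTF, true → SAP | Fall (points) |
|---|---|---|---|
| 2 weeks | 0.23 | 39.3 → 38.8% | about 0.5 |
| 4 weeks | 0.46 | 39.8 → 38.7% | 1.1 |
| 2 months | 1.0 | 40.9 → 38.4% | 2.6 |
| 3 months | 1.5 | 41.9 → 37.8% | 4.2 |

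Falls are typical values over the 0 to 10% efficacy-stop settings. Treatment past progression is not modelled, because SAP 6.3(6) does not define its censoring date.

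**3. First versus last drug stopped.** Two exponential stopping times with hazard λ = ln 2 / 10 per month each (assumed 10-month median), of which a share ρ is common to both drugs.

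- First stop: S_first(t) = exp(−(2 − ρ)λt).
- Both stopped: S_both(t) = 2 exp(−λt) − S_first(t).
- At 12 months exp(−λt) = 2^(−1.2) = 0.435. With ρ = 0.75: S_first = exp(−1.25 × 0.832) = 35.4% and S_both = 87.1 − 35.4 = 51.7%.

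| ρ | First stopped | Both stopped | Gap (points) |
|---|---|---|---|
| 90% | 40.1% | 47.0% | 7 |
| 75% | 35.4% | 51.7% | 16 |
| 50% | 28.7% | 58.3% | 30 |
| 0% (extreme) | 18.9% | 68.1% | 49 |

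For medians of 8 to 20 months the gap is 13 to 16 points at 75% shared and 5 to 7 at 90%.

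**4. Yardstick.** In 2,000 samples of 70 patients (exponential, median 9.1 months, Greenwood variance), the 12-month 95% confidence half-width averages 12.8 points.

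**The case against.** The best defence is one of weight. TTF is secondary and descriptive, with no test. The frequency of efficacy stops is unknown, and if there are none this censoring changes nothing. The two censoring effects oppose each other: under the assumptions above their net effect at 12 months runs from about −4 to +2 points, well inside the confidence interval. Protocol 9.7 allows the SAP to change a secondary endpoint, and not counting a stop for good response as a failure is a possible analytic choice. The term may be a translation slip; pairing it with progression-free patients suggests good response more than lack of efficacy. The word *earlier* in the protocol's definition could also point to the first drug stopped.

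Most of this stands as a limit on size. The lack-of-efficacy figures are a scenario that no passage supports directly. The small end of the censoring-date effect is plausible, because Protocol 9.1.3.2 allows non-radiological assessment of progression and SAP 8.3.2 works on a 2-week avelumab cycle. The large first-versus-last gaps depend on assumed shared hazards and do not come from the efficacy-stop rule.

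It does not remove the fault. Permission to modify does not cover a change that is neither defined nor declared. The word *earlier* has no clear referent in the protocol's sentence, and the SAP writes *and/or* where it could have settled the matter.

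**Conclusion.** The concern holds and should be fixed. The undeclared efficacy-stop censoring is wrong as written, on the text alone. Its effect is conditional on such stops occurring and is probably small: 1 to 3 points at 12 months for about 1 to 2 of 70 patients, and up to about 6 if the term takes in a quarter of progression-driven stops. The censoring date is unsuitable and biases the other way, so no net direction can be stated. The combination end date is an ambiguity, and potentially the largest item: at 75% shared hazard its 16-point gap exceeds the half-width of about 13. Every size rests on assumed rates. The baseline description that forms the primary endpoint is untouched.

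**What to change.** Before data lock, as Protocol 9.7.4 requires for fixing the SAP, revise the three TTF rows of SAP 6.3(1):

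- **Event:** permanent end of treatment for any reason, or death, whichever comes first.
- **Censoring:** only patients still on treatment, at the last date known to be on treatment and no later than 20 June 2021, regardless of progression status.
- **Combination row:** one end-date rule, either first drug stopped or both stopped. The alternative as a sensitivity analysis is optional.
- **If efficacy-stop censoring is kept:** define the term, list the change in SAP Section 9, and report the any-cause analysis beside it.

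These changes concern the analysis only. The cost is SAP wording and minor programming. Protocol 9.3.5 and 9.3.6 already collect administration dates and reasons for discontinuation, and SAP 8.3.6 already uses date of death, first-line treatment status and the reason for discontinuation.

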### **8.2. Secondary objectives**

- 1) To evaluate the efficacy of avelumab plus axitinib combination therapy for patients with mRCC treated in Japan.
- 2) To describe clinical usage of corticosteroid for immune-related adverse events (irAE) during avelumab plus axitinib combination therapy period.
- 3) To describe pre-treatment and treatment for infusion-related reaction of avelumab.
- 4) To describe patterns of post progression subsequent treatments.

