#### **9.1.3.3. Objective response (OR)**

OR is defined as the following:

- Complete or partial response as the best adjudication result (complete response [CR] > partial response [PR] > stable disease [SD] > progressive disease [PD], unknown) in a method complies with RECIST version 1.1 tumor assessment as closely as possible in clinical practice by investigator's judgment.

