### **9.3.4. Clinical outcome (OR)**

Definitions of OR is defined in [Section 9.1.3](#). The following data will be collected to determine the clinical outcomes: tumor assessment (CR, PR, SD, PD, and unknown)

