### **9.3.9. Second-line regimen after avelumab plus axitinib treatment**

The following second-line regimen data will be collected: medication after avelumab plus axitinib treatment.

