4 SUMMARY OF STUDY DESIGN

1) Objective

(1) Primary objective

To describe the demographic and baseline characteristics of patients with mRCC treated with avelumab plus axitinib as a first-line therapy in a real-world clinical setting.

(2) Secondary objective

1. To evaluate the efficacy of avelumab plus axitinib combination therapy for patients with mRCC treated in Japan.
2. To describe clinical usage of corticosteroid for immune-related adverse events (irAE) during avelumab plus axitinib combination therapy period.
3. To describe pre-treatment and treatment for infusion-related reaction of avelumab.
4. To describe patterns of post progression subsequent treatments.

2) Study design

This study is a multicenter, non-interventional, retrospective, medical chart review of patients with mRCC treated with avelumab plus axitinib as a first-line therapy in Japan between 20 December 2019 and 20 December 2020. All decisions regarding clinical management and treatment of the participating patients were made by the investigator as part of standard care in real-world clinical settings and were not contingent upon the patient's participation in the study. Data will be collected if available per study site.

- Index date: The date of first prescription for avelumab plus axitinib between 20 December 2019 (launch date) and 20 December 2020
- Observation period: Patients will be followed from index date to 20 June 2021

3) Study drug

Avelumab (BAVENCIO®)

4) Inclusion and exclusion criteria

➤ Inclusion criteria

Patients must meet all of the following inclusion criteria to be eligible for inclusion in the study:

- 1) Diagnosed with mRCC based on the General Rule for Clinical and Pathological Studies on Renal Cell Carcinoma (4th Edition) before receiving avelumab plus axitinib as a first-line therapy;
- 2) Over 20 years of age at the time of mRCC diagnosis;

- 3) Start treatment with avelumab plus axitinib as a first-line therapy for mRCC from 20 December 2019 to 20 December 2020;
- 4) For patients who are still alive and have routine visits to the study site, evidence of a personally signed and dated informed consent document indicating that the patient has been informed of all pertinent aspects of the study. For patients who are still alive and had been transferred to another hospital, evidence that the patient has been informed of all pertinent aspects of the study and oral or written informed consent is obtained.

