8.3.1.3 Objective Response: OR

Analysis set	Analysis population
Details of analysis	
Tabulate the best overall response by presence of confirmed BOR, あ all patients, and evaluation method (RECIST and non-RECIST).
 
In addition, calculate the number and proportion of patients with ORR and its 95% confidence interval.

Supplement	<Calculation method for each 95% confidence interval>

ORR:Clopper-Pearson confidence interval

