8.3.5 Subsequent treatment-related endpoints

Analysis set	Analysis population
Details of analysis	Calculate summary statistics by drug for duration of subsequent treatment following avelumab plus axitinib treatment.

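### The SAP's ORR window runs to the data cut-off with no stop at subsequent therapy, so a second-line response, if recorded, would count for avelumab plus axitinib

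*SAP*

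**What the plan says.** SAP 6.3(2) takes ORR as the share of patients whose CR or PR is "the best overall response in tumor assessment during the observation period", assessed by an investigator in practice. SAP section 4 fixes that period by calendar date: "Observation period: Patients will be followed from index date to 20 June 2021". Protocol 9.1 says the same.

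The other places that deal with response are:

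- Protocol 9.1.3.3 defines OR as a best result of CR or PR, judged by the investigator "in a method complies with RECIST version 1.1 tumor assessment as closely as possible in clinical practice". It gives no time window.
- Protocol 9.3.4 lists the data to be collected as "tumor assessment (CR, PR, SD, PD, and unknown"). It lists no assessment date and names no line of treatment.
- SAP 8.3.1.3 tabulates best response by confirmation status, for all patients, and by "evaluation method (RECIST and non-RECIST"). It has no split or cut by line of treatment.

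On second-line treatment, Protocol 9.3.9 says "The following second-line regimen data will be collected: medication after avelumab plus axitinib treatment", and the planned analysis in SAP 8.3.5 is "Calculate summary statistics by drug for duration of subsequent treatment following avelumab plus axitinib treatment".

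**The concern.** ORR serves the secondary objective "To evaluate the efficacy of avelumab plus axitinib combination therapy for patients with mRCC treated in Japan". A response that first appears on a later regimen says nothing about that combination. The written window nevertheless stays open after avelumab plus axitinib has ended, up to the cut-off. A patient with SD or PD on first line and a PR on second line before 20 June 2021 would meet the definition of a responder as it stands.

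An error of this kind can only raise ORR. The planned Clopper-Pearson interval would not reveal it, because that interval describes sampling error and takes the responder count as correct. The stakes are limited: ORR is one of several secondary endpoints, the study is descriptive, and no hypothesis is tested (Protocol 9.5).

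**Working it through.** The plan states no ORR, second-line response rate or sample-size calculation to reproduce. The check is therefore a comparison of wording, followed by simple arithmetic on what one misattributed response would do.

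**1. How long the window is.** Index dates run from 20 December 2019 to 20 December 2020 and the cut-off is 20 June 2021. SAP 6.2 sets 1 month = 30.4375 days.

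- Earliest index date: 548 days; 548/30.4375 = 18.0 months.
- Latest index date: 182 days; 182/30.4375 = 6.0 months.

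The length depends only on the index date, not on treatment status. SAP 8.3.5 plans to summarise how long subsequent treatment lasted, so the plan itself expects some second-line time.

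**2. What ties each endpoint to first-line treatment.**

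| Endpoint | Tie to first-line treatment | Where |
|---|---|---|
| Real-world PFS | Censored at start of subsequent treatment | SAP 6.3(1); also Protocol 9.1.3.2 |
| TTF of the combination | Labelled first-line; ends with the study drugs | Protocol 9.1.2; SAP 6.3(1), 8.3.1.1 |
| Corticosteroid endpoints | Tied to the period of study-drug treatment | Protocol 9.1.2; SAP 8.3.3 |
| OR / ORR | None stated | Protocol 9.1.3.3, 9.3.4; SAP 6.3(2), 8.3.1.3 |

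Of these endpoints, OR/ORR alone has neither a first-line label nor a stop.

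**3. Whether RECIST supplies the stop.** It does not do so in writing. The protocol asks for RECIST 1.1 only as far as practice allows, and the SAP also tabulates assessments made by other methods. No cut-off is stated for either kind.

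**4. Effect per response.** Let k be the number of first-line non-responders with a recorded second-line CR or PR, and N = 70 the expected number of patients (Protocol 9.5), all in the denominator. The rise in ORR is 100 × k/N percentage points.

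- k = 0: 0
- k = 1: 100 × 1/70 = 1.4
- k = 2: 100 × 2/70 = 2.9
- k = 3: 100 × 3/70 = 4.3

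These values of k are illustrative. The documents do not say which applies, and k = 0 is possible.

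**5. What the interval does.** Assume, for illustration only, 28 first-line responders among 70. The 95% Clopper-Pearson results are:

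- k = 0: 28/70 = 40.0% (28.5 to 52.4)
- k = 1: 29/70 = 41.4% (29.8 to 53.8)
- k = 3: 31/70 = 44.3% (32.4 to 56.7)

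The whole interval moves up with the estimate. Its half-width is about (52.4 − 28.5)/2 = 12 points, so one or two such responses would be small beside the sampling error.

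**The case against.** The strongest reply is that no harm has been shown. No section says that tumor response on second-line treatment is collected. What is listed points the other way: medication only in the protocol, duration by drug in the SAP. The research question, the objective and the neighbouring TTF endpoint all concern first-line treatment, so an investigator asked for best response would naturally give the response to that regimen. Protocol 9.1.3.3 and 9.3.4 also fit a single investigator-judged best response per patient. On that reading no programmer searches dated scans, and the SAP phrase merely notes the data cut-off.

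Most of this stands as a limit on impact. It does not repair the definition. The SAP states a window, that window is wider than the objective, and nothing tells a site to stop at first line. With no separate second-line response item listed, the one undated tumor-assessment item is also the only listed place where such a response could be entered.

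A reader might go further and infer that ORR will be inflated by several points, perhaps sizing this from the 13.8-month median PFS cited in Protocol section 7. The documents do not support that. Patients who have progressed or died are not the pool for second line: Protocol 9.1.3.2 provides for patients who start a next line with no recorded progression, and patients who die may never start one. The share starting second line, the share assessed, the response rate there and the share entered in the response item are all unknown.

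One could also argue for ending the window at first progression if that is earlier. That version removes second-line responses too, but it additionally drops any response after progression while the patient is still on the combination. This is a separate choice, not needed to settle attribution.

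**Conclusion.** The point holds as a flaw in the written definition: ORR is meant to describe the combination, but its window does not end when another therapy begins. It does not hold as a demonstrated bias. The effect is zero if the CRF item holds first-line responses only. Otherwise it is 1.4 points upward per misattributed patient, assuming 70 patients in the denominator, with an unknown total. Because the endpoint is secondary and descriptive, and the consequence depends on CRF wording that the documents do not show, this is a minor point and a cheap improvement.

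**What to change.** In SAP 6.3(2), applied in 8.3.1.3, define best overall response as the best tumor assessment from the date of initial dose to the earlier of the start of subsequent anticancer therapy or 20 June 2021. This is the treatment stop already used for real-world PFS, so the start date of subsequent treatment is needed in any case.

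Before data lock, check the CRF response item:

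- If it is limited to first-line treatment, or is dated so that the rule can be applied, no queries are needed.
- If it is neither, query sites only about responders who started subsequent therapy.
- Where the timing stays unknown, report how many patients are affected and give ORR with and without them.

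**Cost.** One sentence in the SAP and one CRF check. Protocol 9.7 lets the SAP modify the protocol's plans and asks for an amendment only for major changes to primary endpoints, so none is needed. Protocol 9.7.4 requires the SAP to be fixed before data lock, so the change must come before then. The sentence alone cannot be applied if the item is undated, and Protocol 9.3.4 lists no assessment date, so some queries may be unavoidable. Protocol section 6 plans the end of data collection and the dataset lock for the same day, 31 January 2022, which leaves no gap between them; queries would have to be raised and closed before that date. The reported ORR may also be slightly lower.
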